Aim 2: Determine the minimum locomotor training *duration* needed to maximize immediate improvements in walking capacity. *Hypothesis* (based on our preliminary data¹⁵): Compared with 4 & 8 weeks of HIT, 12 weeks of HIT will elicit significantly greater improvements in walking capacity and increased benefit over MAT. However, if effects peak earlier than 12WK, it would provide scientific justification to keep testing a shorter, lower-cost protocol to determine its sustained effects relative to longer training durations.

These aims will provide foundational information to guide dosing of locomotor training intensity and duration in future studies and clinical practice. Further, the expected outcomes offer the potential to transform current stroke rehabilitation and make a positive impact on the disability burden of stroke.

[figure not shown]
B. BACKGROUND AND SIGNIFICANCE

Stroke is a leading cause of chronic disability¹ and limited walking capacity is a major barrier to stroke recovery.⁸ Despite declining mortality rates from stroke, 795,000 people continue to experience a stroke in the United States each year, resulting in 6.6 million Americans (2.6% of adults) currently living with the chronic sequelae of stroke.¹ In addition, the chronic disability and financial burden associated with stroke are expected to continue to increase, due in part to the aging population.^{1,16} While the majority of persons in the chronic phase of stroke are able to walk without continuous physical assistance from another person,^{2,3} less than 10% have adequate walking capacity (speed and endurance) to allow normal daily functioning (e.g. work, grocery shopping).^{4,5} On average, community dwelling stroke survivors are able to walk about 0.5 m/s over short distances and 250 meters in 6 minutes,^{4,17-19} representing only ~40% of age-predicted normal gait speed and capacity (1.3 m/s and over 500 meters, respectively).²⁰⁻²² This inadequate recovery of walking is devastating because it leads to a loss of life roles, social isolation, dependency, sedentary lifestyle and increased risk for secondary cardiovascular events.^{2,4-6,8,20,23-25} Therefore, improved walking capacity is a primary goal of stroke rehabilitation.^{8,26} *Relevance:* This project targets walking capacity limitations for persons with chronic stroke.

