The proposed study builds on our previous work and overcomes the limited scientific rigor of previous studies with a high-quality, moderately-sized, 3-site RCT, using our novel HIT protocol to ensure vigorous training intensity and a best-practice MAT control group. This study will determine the optimal training intensity and minimum training duration needed to maximize immediate improvements in walking capacity and other measures (gait speed, aerobic fitness, metabolic cost of gait, daily walking activity and quality of life) among chronic stroke survivors. This will be the first study designed to compare HIT and MAT in chronic stroke and the first study in any population to compare different HIT durations. Aim 1 is expected to provide proof of concept that vigorous training intensity is a 'critical ingredient' for locomotor recovery, by showing that HIT elicits significantly greater immediate improvement in walking capacity compared with MAT, using a clinically feasible 4-week training dose. Aim 2 is expected to show that longer durations of HIT elicit continued significant improvements, approaching normal walking capacity, with increasing benefit over MAT across 12 weeks of training. However, if effects peak earlier than 12 weeks, it would provide scientific justification to keep testing a shorter protocol that is more aligned with patient preferences and current reimbursement models.

[figure not shown]

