H_{1a} will be tested by the significance of the [group x time] contrast from Baseline to POST-4wk for the 6-minute walk test at $\alpha=0.05$. For H_{1b}, secondary outcomes will be tested separately using the same model as H_{1a} to identify the most sensitive measures to carry forward into future studies.¹¹⁰ The Benjamini-Hochberg procedure²²³ will be used to control the false discovery rate (FDR) for the secondary outcomes.

Aim 2: Determine the minimum locomotor training duration needed to maximize immediate effects

Hypothesis 2a (H_{2a}): Within the HIT group, *walking capacity* (6 minute walk test distance) and *secondary outcomes* will significantly increase from 4WK to 8WK and from 8WK to 12WK

Hypothesis 2b (H_{2b}): Compared to MAT, HIT will elicit significantly greater improvements in *walking capacity* and *secondary outcomes* from PRE to 8WK and from PRE to 12WK

H_{2a} will be tested by the significance of the respective time contrasts within the HIT group. **H_{2b}** will be tested by the significance of the respective [group x time] contrasts. Secondary outcomes will have FDR control.²²³

Data and Safety Monitoring Plan

An adverse event (AE) is an undesired medical occurrence in a participant who is undergoing study procedures and does not necessarily have a causal relationship with the treatment or study procedures. This includes any adverse clinical change that occurs at any time following consent. A serious AE (SAE) is any adverse experience occurring during study participation that results in any of the following outcomes: death; a life threatening situation; inpatient hospitalization or prolongation of existing hospitalization; a persistent or significant disability/incapacity.^{209,210} The data and safety monitoring plan for this study will include participant monitoring for AEs and other problems, review of AEs and other problems by the study team and IRB, and an independent data safety monitoring board (DSMB).

Participant safety monitoring

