Statistical Analysis Plan

NCT03760016

Moderate-Intensity Exercise Versus High-Intensity Interval Training to Recover Walking Post-Stroke

Finalized on 08-07-2020. Uploaded to ClinicalTrials.gov on 04-13-2021, prior to completion of data collection and prior to any outcome data analysis.

Overall Statistical Methods

SAS will be used for data analysis, and the study statistician will remain blinded to study group. Data related to baseline variables, intervention fidelity and concurrent outside interventions will be compared between groups using t-tests and χ^2 . If a baseline prognostic factor is found to differ between groups, it will be considered for inclusion as a covariate during hypothesis testing. The primary analysis will follow intent-to-treat methods and any missing data will be handled with the maximum likelihood method, assuming that patterns of missingness do not violate the missing at random assumption.¹ To test robustness of different ways to handle missing data, sensitivity analyses will be used.

Hypothesis Testing

Hypothesis 1: To test our primary hypothesis that, compared with 4 weeks of MAT, 4 weeks of HIT will elicit significantly greater improvement in the 6MWT distance, a general linear model will be used. In this model, we will use fixed effects for group (HIT, MAT), time (PRE, 4-WK, 8-WK, POST), [group x time], site (UC, KUMC, UD), [site x time], baseline speed category (<0.4 , ≥ 0.4 m/s), and [baseline speed category x time] with an unstructured covariance matrix. This hypothesis will be tested by the significance of the [group x time] contrast from the PRE to 4-WK for the 6MWT at $\alpha=0.05$. Secondary outcomes will be tested separately using this same model to identify the most sensitive measures to carry forward into future studies.² The Benjamini-Hochberg procedure³ will be used to control the false discovery rate for the secondary

outcomes, which include: comfortable gait speed, fast gait speed, VO_2 at the ventilatory threshold and the PROMIS-Fatigue Scale total score.

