Hypothesis 2: To test the hypothesis that, compared with 4 and 8 weeks of HIT, 12 weeks of HIT will elicit significantly greater improvements in walking capacity and increased benefit over MAT, the same general linear model described above will be used. The hypothesis that 12 weeks of HIT will elicit greater improvements in primary and secondary outcomes compared to 4 and 8 weeks of HIT will be tested by the significance of the respective time contrasts within the HIT group. The hypothesis that HIT will elicit significantly greater improvements in primary and secondary outcomes from PRE to 8-WK and PRE to POST compared to MAT will be tested by the significance of the respective [group x time] contrasts. False discovery rate control will be applied for secondary outcomes.³

Prognostic Factor Testing

We will also test for baseline cofactors that may influence a stroke survivor's response to the interventions in this study. To do this, we will utilize a multivariate prognostic model that includes comfortable gait speed, lower extremity Fugl-Meyer motor scores, and scores on the Activities-Specific Balance Confidence Scale. These measures were selected based on previous studies suggesting that comfortable gait speed,⁴⁻⁹ lower limb Fugl-Meyer motor scores,⁹⁻¹¹ and balance abilities¹² may influence response to gait rehabilitation interventions in individuals with chronic stroke. Other potential cofactors will also be explored to inform future studies.

Safety Data Analysis

We expect a similar rate of non-serious adverse events (AEs) between HIT and MAT (e.g. temporary exercise-related soreness and fatigue), without any study-related serious AEs. In the unexpected event of one or more serious adverse events (SAE), the SAE rate will be compared between groups to confirm that there is no significant difference in major safety risk between HIT and MAT. A logistic regression model will be used for this analysis with SAE (yes/no) as the dependent variable and fixed effects for group, site, and baseline gait speed category. If there are SAE(s) in one group only, a continuity correction (0.5 SAEs added to each group) will still allow the odds ratio to be calculated.¹³

References

2. Dobkin BH. Progressive Staging of Pilot Studies to Improve Phase III Trials for Motor Interventions. *Neurorehabil Neural Repair*. 2009;23(3):197-206.

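### SAP Hypothesis 2 claims that HIT's benefit over MAT increases with training duration, but no planned contrast tests whether the HIT-MAT gap grows after 4 or 8 weeks

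*SAP*

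**What the plan says.** **The claim.** SAP Hypothesis 2 states that, relative to 4 and 8 weeks of HIT, "12 weeks of HIT will elicit significantly greater improvements in walking capacity and increased benefit over MAT". The Aim 2 hypothesis in protocol section A uses the same words. Protocol section B expects Aim 2 to show that "longer durations of HIT elicit continued significant improvements, approaching normal walking capacity, with increasing benefit over MAT across 12 weeks of training".

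**The between-group tests.**
- The primary hypothesis in the SAP is "tested by the significance of the [group x time] contrast from the PRE to 4-WK for the 6MWT".
- For Hypothesis 2, the SAP says that HIT's "improvements in primary and secondary outcomes from PRE to 8-WK and PRE to POST compared to MAT will be tested by the significance" of the corresponding group-by-time contrasts.
- Protocol E.2, H2b, likewise compares the arms "from PRE to 8WK and from PRE to 12WK".

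**The within-HIT tests.** Protocol H2a states that outcomes in the HIT arm "will significantly increase from 4WK to 8WK and from 8WK to 12WK", and this "will be tested by the significance of the respective time contrasts within the HIT group". The SAP compares 12 weeks with 4 and with 8 weeks, again inside the HIT arm only.

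**The planning values.** Protocol E.2, Sample Size, assumes a 6MWT gain of 15 m per 4 weeks on MAT and 35 m per 4 weeks on HIT.

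**The concern.** An increased benefit over MAT, relative to 4 and 8 weeks, is a statement about change in the between-group difference. Each planned between-group contrast starts at PRE, so each asks only whether that difference is above zero at one visit. The within-HIT contrasts show whether HIT keeps improving, but they cannot show whether it improves faster than MAT. MAT also trains for all 12 weeks and is itself expected to keep gaining.

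One clause of the Aim 2 hypothesis could therefore be reported as supported without having been tested. Section A says the aims are meant to guide the dosing of intensity and duration in later studies and in practice, so the clause has consequences.

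**Working it through.** **1. What is claimed and what is tested.** Let H(t) be the mean HIT change from PRE, M(t) the mean MAT change, and D(t) = H(t) − M(t).

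| | Quantity |
|---|---|
| Claimed growth | D(12) − D(4) > 0 and D(12) − D(8) > 0 |
| Tested between groups | D(4) = 0, D(8) = 0, D(12) = 0 |
| Tested within HIT, protocol | H(8) − H(4), H(12) − H(8) |
| Tested within HIT, SAP | H(12) − H(4), H(12) − H(8) |

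No tested quantity is a difference between two values of D.

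**2. A counterexample.** Take HIT +35/+50/+65 m and MAT +15/+30/+45 m at 4/8/12 weeks. Then D = 20/20/20 m and HIT gains 15 m in each later block. Every tested quantity is positive, yet D(12) − D(4) = 0. No SD is needed for this step.

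**3. The plan's own expectation.** With +35 m and +15 m per 4 weeks, H = 35/70/105 and M = 15/30/45, so D = 20/40/60 m. The plan expects the gap to widen by 40 m between 4 and 12 weeks. That widening is what goes untested.

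**4. Inputs for an illustration.** The available text gives no SD or base correlation, and Figure 6 is not shown, so the target of 40 participants for at least 80% power cannot be reproduced. It can only be inverted. By the normal approximation, SD of PRE-to-4WK change = 20 / [(1.960 + 0.842) × √(2/20)] = 22.6 m. With a t distribution on 35 df (40 participants less 5 between-subject parameters) it is 21.9 m. SDs of 22, 30 and 40 m were assumed.

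Other assumptions:
- 20 per arm, complete data, marginal SD 100 m (80 or 120 m moves results by under 1 point).
- Correlation exponents 1, 1.25 and 1.5 for lags 1 to 3, from the protocol's decay rate of 0.5.
- Between-group t on 35 df and within-HIT paired t on 19 df.
- A pass is two-sided p < 0.05 in HIT's favour.

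The SD of the two-block change follows. At 22 m, ρ = 1 − 22²/(2 × 100²) = 0.9758, and √[2 × 100² × (1 − 0.9758^1.25)] = 24.6 m. For 30 and 40 m it is 33.4 and 44.5 m.

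**5. How often all Aim 2 6MWT tests pass** (200,000 simulated trials per cell; protocol / SAP contrasts, %).

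| True pattern | SD 22 | SD 30 | SD 40 |
|---|---|---|---|
| Gap constant at 20 m, both arms +15 m per later block | 40.0 / 46.4 | 10.9 / 17.5 | 2.3 / 5.8 |
| Same, PRE-4WK also required | 36.1 / 42.4 | 7.9 / 14.0 | 1.2 / 4.0 |
| Same, Aim 2 set plus group x (12WK−4WK) | 2.0 / 2.0 | 1.2 / 1.3 | 0.5 / 0.7 |
| Gap constant at 20 m, both arms +8.3 m per later block | 6.4 / 20.3 | 1.2 / 6.0 | 0.3 / 1.8 |
| Gap shrinking 20/15/10 m (HIT +35/+45/+55, MAT +15/+30/+45) | 5.7 / 10.7 | 1.1 / 3.6 | 0.3 / 1.2 |

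The 8.3 m row spreads the +25 m that the protocol cites as previously observed evenly over three blocks, which is an assumption. In the first pattern the two H2b contrasts alone both pass in 53.6%, 28.0% and 14.6% of trials. If both arms plateau after 4WK, the set passes in at most 0.35%. If the arms are parallel from PRE, it passes in at most 0.66%.

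**6. Power of the missing contrasts** (SD 22 / 30 / 40 m).

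| True gap | 12WK−4WK | 12WK−8WK | Both |
|---|---|---|---|
| 20/40/60 m (the plan) | 99.9 / 95.7 / 78.9% | 79.9 / 53.4 / 33.5% | 79.9 / 53.0 / 31.7% |
| 20/30/40 m | 70.6 / 45.1 / 28.1% | – | 26.1 / 13.6 / 7.5% |

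**The case against.** **The operational hypotheses match their tests.** H2b claims only greater improvement from PRE to 8 and to 12 weeks, and its contrasts test exactly that. The wording about increased benefit sits in the aim statement, the background and the SAP's opening sentence, so it may be loose shorthand for H2b. This stands for H2b. It does not rescue the opening sentence, which makes 4 and 8 weeks of HIT the comparator and so reads as a claim of growth.

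**The main decision in Aim 2 is safe.** Section A says that "if effects peak earlier than 12WK, it would provide scientific justification to keep testing a shorter, lower-cost protocol". That turns on whether HIT's own effect peaks, which the within-HIT contrasts address. This is correct, and it limits the concern to one clause.

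**The percentages are soft.** They rest on assumed SDs, and neither document requires all tests to pass jointly. The simulation covers only the 6MWT, not the secondary outcomes under false discovery rate control. It uses 20 per arm, whereas the protocol plans to enrol 50 to 75. All of this is true. A larger sample does not help: at 25 per arm, the SAP set passes under the constant gap in 61%, 27% and 10% of trials. The gap in the plan itself depends on none of these numbers.

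**The remedy is partial and adds a test.** Making only 12WK−4WK decisive leaves the 8-week comparison to an interval, and the new test is at an unadjusted 0.05. Both points are fair. The choice follows from the power of the 8-week contrast. Requiring the new contrast for a growth claim makes that claim harder to reach.

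**Conclusion.** The concern holds. The claim that HIT's benefit over MAT increases with duration has no planned test, and this follows from the wording of the two documents alone. False support needs the arms to separate by 4WK and then both keep gaining. Under a constant 20 m gap with 15 m gains per later block, it ranges from 2.3% to 46.4% across the assumed SDs and the two sets of within-HIT contrasts. It is rare if both arms plateau or run parallel from PRE. These rates are illustrative only. The primary PRE-to-4WK test, H2b as worded and the within-HIT question of an early peak are unaffected. The point should be fixed, because it changes what Aim 2 can conclude about duration.

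**What to change.** Choose one of two changes.

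**Option 1: test the growth.** Add to SAP Hypothesis 2 and protocol H2b: *Increased benefit over MAT in the 6MWT will be tested by the group x (12WK−4WK) contrast from the same model at two-sided 0.05; the group x (12WK−8WK) contrast will be reported as supportive; both with 95% confidence intervals.*
- Claim growth relative to 4 weeks only if 12WK−4WK is significant in HIT's favour, and describe the 8-week comparison from its interval.
- Keep the PRE-anchored contrasts as tests of benefit at each duration.
- Apply the new contrasts to secondary outcomes only within the planned false discovery rate control.
- State that a null result does not show that longer training adds nothing, because MAT also trains for 12 weeks.

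Time is already categorical with an unstructured covariance, so this costs two ESTIMATE statements and a few sentences, with no new data or visits.

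**Option 2: drop the growth claim.** Reword the Aim 2 hypothesis in protocol section A, the expectation in section B and the opening of SAP Hypothesis 2 to a benefit over MAT at 8 and 12 weeks. This costs only text.

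As a separate and minor matter, reconcile the within-HIT contrasts: the protocol tests 4 to 8 and 8 to 12 weeks, the SAP 4 to 12 and 8 to 12.

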Regardless of the outcomes, our aims will provide fundamental new knowledge to inform selection of intensity and duration dosing parameters for aerobic training and gait recovery interventions post-stroke. At the same time, this study will provide all remaining needed data to justify and design a subsequent definitive trial to determine the relative efficacy of HIT and MAT for eliciting clinically meaningful and sustained improvements in walking function. Therefore, *the proposed study is significant because it is expected to constitute a critical step in a continuum of research that will lead to the clinical implementation of novel training strategies to synergistically and potently address both gait impairment and aerobic deconditioning post-stroke*. This research will likely have a major impact on the massive¹¹² disability and financial burden of stroke, because, unlike the currently recommended protocol for addressing these outcomes (MAT),^{33,46,50-52,60-62} HIT appears to provide meaningful benefits with a training duration that fits well within current clinical practice models and patient preferences.^{66,67,113} By elucidating the relative time course of changes in different outcomes, the data from this study will also inform future mechanistic and biomarker investigations in our team member's areas of expertise, including brain connectivity, neurophysiology, molecular genetics and vascular function. In addition, the data will be made publicly available after study completion to support further exploration and meta-analysis.

C. PRELIMINARY STUDIES

Our team developed a novel treadmill HIT protocol that enables persons with chronic stroke to achieve vigorous aerobic intensity (a mean 76% HRR) and fast treadmill speeds (a mean 178% of fastest floor speed) in the first session.¹² This initial HIT protocol was developed by examining the influence of recovery period duration on treadmill speed and aerobic intensity (Figure 2).¹² The shortest recovery duration used in previous studies (120 seconds)^{81,82} was suboptimal. R60 (60 second recovery) elicited the greatest immediate changes in treadmill speed while 30 second recovery elicited the highest aerobic intensity and enabled all 18 participants to achieve vigorous intensity ($\geq 60\%$ HRR/VO₂-peak).

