The primary general linear model for both Aims will include fixed effects for intercept, group (HIT, MAT), time (PRE, 4WK, 8WK, 12WK), [group X time], site (UC, KUMC, UD), [site x time], baseline gait speed category (<0.4, ≥0.4 m/s) and [baseline gait speed category x time] (to account for the stratification factors)^{218,222} with an *unstructured covariance matrix* (to account for the repeated nature of the data without making assumptions about covariance patterns).²¹⁸ Time will be modeled as a categorical factor (i.e. analysis of response profiles²¹⁸), since there is no available information about the expected pattern in the HIT mean response over time.

Sample Size

This study is powered to detect the minimal clinically important difference (MCID) of 20 meters in walking capacity (6-minute walk test) change²²⁰ between groups.

GLIMMPS²²¹ was used to estimate the sample size needed to detect a significant [group x time] effect at each time point, using the model above with a two-sided α of 0.05. The 6-minute walk test change estimate for the MAT group (+15 m / 4 wks) was taken from our 4-week pilot study⁹ and resulted in a 12WK change estimate (+45 m) somewhat larger than previously observed (+25 m).⁶⁰ In contrast, the HIT group estimate (MAT group change plus MCID = +35 m / 4 wks) was notably lower than observed in our most recent 4-week pilot study (+115 m in 4 wks), indicating that the true effect size may be much larger and easier to detect than the MCID. Variance & covariance parameters for each time point were estimated by pooling data across our two previous 4-week studies (n=20), using the mean variance for each time point and the highest suggested exponential decay rate (0.5)²²¹ for the repeated measures correlations involving 8WK and 12WK. These calculations indicated a target sample size of 40 (20/group) for ≥80% power (Fig 6). *To conservatively account for attrition, we plan to enroll at least 50 and up to 75 participants.*

Hypothesis Testing

Aim 1: Determine the optimal locomotor training *intensity* for eliciting immediate improvements in walking capacity among chronic stroke survivors

Hypothesis 1a (H_{1a}): Compared with MAT, HIT will elicit significantly greater improvement in walking capacity (6-minute walk distance) from PRE to 4WK (*primary study hypothesis*)

Hypothesis 1b (H_{1b}): Compared with MAT, HIT will elicit significantly greater improvement in secondary outcomes from PRE to 4WK

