The DSMB will consist of at least 3 members separate from the study team, including at least one physician and at least one biostatistician, with collective experience in the management of patients with stroke, exercise and clinical trials. A quorum will require at least 2 members, including the chair. Persons with a significant conflict of interest (financial, institutional or scientific) will not be permitted to be DSMB members. The DSMB will meet at least (approximately) annually. A summary report will be sent to the DSMB prior to each meeting, including safety and clinical outcome data. DSMB meetings will include open sessions where the DSMB may discuss any issues with the study team and closed sessions where the DSMB alone decides on its recommendations. The DSMB will assess the risks and benefits of study participation for all participants and will provide a written report of their analyses and recommendation as to whether the study should continue, whether modifications to the study are needed or if the study should be terminated. These reports will be sent to the investigators and the IRB.

Safety Data Analysis

In the unexpected event of one or more SAEs, the SAE rate will be compared between groups to confirm that there is no significant difference in major safety risk between HIT and MAT. This analysis will use a logistic regression model with SAE (yes/no) as the dependent variable and fixed effects for group, site and baseline gait speed category. If there are SAE(s) in one group only, a continuity correction (0.5 SAEs added to each group) will still allow the odds ratio to be calculated.⁹ Secondary safety outcomes (different grades/categories of AEs) will be tested using the same model, with [# AEs / # training sessions] as the dependent variable.⁹

E.3. Data Storage and Confidentiality

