Table 7. Adverse Events (AEs) in Pilot RCT

Data reported as no. of participants with AE (total no. of AEs) [AE incidence rate per 100 sessions]

	HIT (n=13, sessions=141)	MAT (n=5, sessions=60)	HIT/MAT AE odds ratio (95% CI)
Any AE	9 (21) [14.9]	4 (8) [13.3]	1.14 (0.47-2.73)
Related to intervention	6 (13) [9.2]	1 (4) [6.7]	1.42 (0.44-4.55)
-Grade 1 (mild)	5 (10) [7.1]	1 (3) [5.0]	1.45 (0.38-5.47)
-Grade 2 (moderate)	2 (3) [2.1]	1 (1) [1.7]	1.28 (0.13-12.59)
-Grade 3-5 (severe-death)	0 (0) [0.0]	0 (0) [0.0]	N/A
-Cardiac disorder	0 (0) [0.0]	0 (0) [0.0]	N/A
-Joint/muscle pain	5 (8) [5.7]	1 (4) [6.7]	0.84 (0.24-2.91)
-Fatigue	3 (3) [2.1]	0 (0) [0.0]	3.03 (0.15-59.56)*
-Nausea	0 (0) [0.0]	0 (0) [0.0]	N/A
-Lightheadedness	1 (2) [1.4]	0 (0) [0.0]	2.15 (0.10-45.43)*
-Other nervous system	0 (0) [0.0]	0 (0) [0.0]	N/A
-Fall	0 (0) [0.0]	0 (0) [0.0]	N/A
-Other injury	0 (0) [0.0]	0 (0) [0.0]	N/A
Unrelated to intervention	6 (8) [5.7]	3 (4) [6.7]	0.84 (0.24-2.91)
-Grade 1 (mild)	5 (7) [5.0]	2 (2) [3.3]	1.51 (0.31-7.51)
-Grade 2 (moderate)	1 (1) [0.7]	2 (2) [3.3]	0.21 (0.02-2.33)
-Grade 3-5 (severe-death)	0 (0) [0.0]	0 (0) [0.0]	N/A
-Atrial fibrillation	1 (2) [1.4]	0 (0) [0.0]	2.15 (0.10-45.43)*
-Other cardiac disorder	0 (0) [0.0]	0 (0) [0.0]	N/A
-Joint/muscle pain	2 (2) [1.4]	1 (2) [3.3]	0.42 (0.06-3.03)
-Fatigue	1 (1) [0.7]	0 (0) [0.0]	1.28 (0.05-31.86)*
-Nausea	0 (0) [0.0]	0 (0) [0.0]	N/A
-Lightheadedness	1 (1) [0.7]	0 (0) [0.0]	1.28 (0.05-31.86)*
-Other nervous system	0 (0) [0.0]	0 (0) [0.0]	N/A
-Fall	1 (1) [0.7]	2 (2) [3.3]	0.21 (0.02-2.33)
-Other injury	1 (1) [0.7]	0 (0) [0.0]	1.28 (0.05-31.86)*

AE odds ratios are from logistic regression modeling of no. of AEs / no. of sessions per participant. CI, confidence interval. *Continuity corrected by adding 0.5 AEs to each group so that AE odds ratios could be calculated. HIT, high-intensity interval training; MAT, moderate-intensity aerobic training

Emergency Response Planning. Although we expect that the study will be safe, we are also well prepared for any unlikely events. AEs will be promptly reported to the IRB and DSMB (see Data and Safety Monitoring Plan above) and referrals for follow up care will be made according to the severity and type of event. Should an emergency medical situation occur during study activities, emergency medical care would be provided and the participant would be transported to the nearest emergency room.

G.2. Potential Benefits

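### The SAE comparison is meant to confirm that the arms do not differ, but it has no margin or interval criterion, and at this trial's size a non-significant result would be inconclusive

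*SAP*

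**What the plan says.** The SAP, under Safety Data Analysis, expects similar rates of non-serious events in the two arms, "without any study-related serious AEs". If one or more SAEs do occur, "the SAE rate will be compared between groups to confirm that there is no significant difference in major safety risk between HIT and MAT". The protocol's section of the same name (E.2) gives the same purpose: "to confirm that there is no significant difference in major safety risk between HIT and MAT".

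Both documents then name the method. It is a logistic regression on SAE yes/no, with fixed effects for group, site and baseline gait-speed category. When only one arm has SAEs, "a continuity correction (0.5 SAEs added to each group) will still allow the odds ratio to be calculated".

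Neither document gives a margin for similar risk, a confidence-interval criterion, an alpha for this comparison, or the test to be applied to the group term (Wald, likelihood ratio or other). Alpha of 0.05 is stated for the 6-minute walk contrast and its sample size. The sample size rests only on a 20 m difference in 6-minute walk change. That gives 20 per group, and to allow for attrition "we plan to enroll at least 50 and up to 75 participants".

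**The concern.** A test for a difference is given the job of showing that there is none. Failing to reject equal risk is evidence of similar risk only when the data also exclude differences that would matter. The plan does not say which differences those are, and does not require the interval that would show whether they are excluded.

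The setting makes this worse. The trial has 25 to 37 participants per arm and few or no SAEs are expected, so non-significance is likely whether or not one arm carries a sizeable excess. If the stated purpose carries through to the report, an inconclusive comparison could be presented as a finding of no difference in major safety risk.

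A second, smaller gap is that the test of the group term is not named. With very few events, Wald and likelihood-ratio tests of the same coefficient can disagree.

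**Working it through.** **Inputs.** Enrolment of 50 to 75 (Protocol, Sample Size) gives about 25 to 37 per arm with equal allocation. The 0.5 correction comes from both Safety Data Analysis sections. Assumptions: two-sided alpha 0.05 (not stated for safety), all enrolled participants analysed, and no adjustment for site or speed category. The documents give no SAE rates, so the SAE counts below are examples.

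**Step 1: reproduce the correction.** Table 7 in protocol section G.1 used the same device on AEs per session. For 3 v 0 events in 141 v 60 sessions, add 0.5 events to each arm and keep the denominators:

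OR = (3.5 × 59.5)/(137.5 × 0.5) = 3.03, 95% CI 0.15 to 59.56.

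For 2 v 0: (2.5 × 59.5)/(138.5 × 0.5) = 2.15, 95% CI 0.10 to 45.43. Both match the table, so this form is used below.

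**Step 2: what a null-looking result leaves open.** Wilson limits for each arm, with z = 1.96:

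(p + z²/2n ± z√[p(1−p)/n + z²/4n²]) / (1 + z²/n)

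Newcombe's interval for d = p1 − p2 runs from d − √[(p1−l1)² + (u2−p2)²] to d + √[(u1−p1)² + (p2−l2)²].

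- 1/25: p = 0.040, limits 0.007 to 0.195. For 1 v 1 the half-width is √(0.033² + 0.155²) = 0.159, so the interval is **-16 to +16 points**.
- 1/37: p = 0.027, limits 0.005 to 0.138. For 1 v 1 the half-width is √(0.022² + 0.111²) = 0.113, so **-11 to +11 points**.
- 3/25: p = 0.120, limits 0.042 to 0.300. For 3 v 1, d = 0.080; lower limit 0.080 − √(0.078² + 0.155²) = -0.094; upper limit 0.080 + √(0.180² + 0.033²) = 0.263. The difference is **8 points (-9 to 26)**.

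**Step 3: the test for 3 v 1 at 25 per arm.** OR = (3 × 24)/(22 × 1) = 3.27, log OR = 1.186. SE = √(1/3 + 1/22 + 1/1 + 1/24) = 1.192, z = 0.995, Wald p = 0.32. The likelihood-ratio statistic is 1.13 on 1 df, p = 0.29. Both are non-significant, while the interval in step 2 reaches 26 points.

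**Step 4: one arm without SAEs, plan's correction applied.** Example for 7 v 0 at 25 per arm: OR = (7.5 × 24.5)/(17.5 × 0.5) = 21.0, log OR = 3.045, SE = √(1/7.5 + 1/17.5 + 1/0.5 + 1/24.5) = 1.494, z = 2.04, p = 0.042.

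| Split | Wald p, 25/arm | LR p, 25/arm | Wald p, 37/arm | LR p, 37/arm |
|---|---|---|---|---|
| 3 v 0 | 0.178 | 0.099 | 0.184 | 0.103 |
| 4 v 0 | 0.118 | 0.045 | 0.126 | 0.048 |
| 6 v 0 | 0.058 | 0.008 | 0.065 | 0.010 |
| 7 v 0 | 0.042 | 0.004 | 0.049 | 0.004 |

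The smallest significant split is 7 v 0 by Wald and 4 v 0 by likelihood ratio at both sizes. For 4, 5 or 6 v 0, the choice of test decides the verdict.

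**The case against.** **The method is named.** A reader might infer that the plan has no statistical method for SAEs. It has one: a covariate-adjusted logistic model, an odds ratio and a rule for a zero arm. Only the test of the group term and its alpha are missing. Fisher's exact test, or a likelihood ratio without the correction, would depart from the plan when one arm has no SAEs, so neither is used above.

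**Nothing says that p > 0.05 will be reported as equal safety.** That is correct. The documents state a purpose and no reporting rule. The team's pilot table already gives counts with odds ratios and 95% CIs, so intervals in the final report are likely. They are not promised for this analysis, and the stated purpose still points the reader to the p-value.

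**Other safeguards exist.** The protocol analyses AE grades and categories per training session and has DSMB review. Both stand, but neither supplies a criterion for concluding that SAE risk is similar.

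**Sizing a trial on its primary outcome is normal.** Agreed. The small sample is no defect in itself; the difficulty is the conclusion asked of it. Power figures are left out because any SAE rates would have to be invented.

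**Downstream harm.** A reader might infer that a mistaken safety verdict would feed directly into the next trial. The protocol (section B) says this study should help to "justify and design a subsequent definitive trial to determine the relative efficacy of HIT and MAT". That sentence concerns efficacy, and the documents do not link the SAE comparison to it.

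**Conclusion.** The concern holds in this limited form. As written in both documents, the SAE comparison asks a difference test to confirm the absence of a difference, without a margin or interval criterion. At 25 to 37 per arm a non-significant result would be inconclusive: differences of 11 to 16 points in either direction remain open at 1 v 1, and of up to 26 points at 3 v 1 with 25 per arm. The unnamed test of the group term can also decide the result in one-sided splits of 4 to 6 events.

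The figures assume equal arms, full follow-up, two-sided 0.05 and no covariate adjustment. Attrition would widen the intervals. The conclusion does not depend on any assumed SAE rate.

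The matter is minor and conditional. It arises only if at least one SAE occurs. It does not affect the primary endpoint, AE monitoring or DSMB review. The documents do not support reading it as a commitment to declare the arms equally safe.

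**What to change.** In the Safety Data Analysis sections of both the SAP and the protocol:

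1. Replace the clause "to confirm that there is no significant difference in major safety risk between HIT and MAT" with: *to estimate the difference in SAE risk between HIT and MAT*.
2. Report SAE counts by arm and the risk difference with a score-based or exact 95% CI. This is in line with the counts and intervals in the pilot's Table 7.
3. State that a non-significant result is inconclusive and is not evidence of equal safety.

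Optionally, if a p-value is kept, name the test of the group term and its alpha.

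The cost is a couple of sentences in each document, with no new data and no change to the sample size. The downside is a more cautious safety conclusion.
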